This study is designed as a prospective, double arm, study. Patients with a diagnosed rupture of the anterior cruciate ligament (ACL) who are scheduled for surgical reconstruction will be considered for enrollment. Eligible subjects will be allocated to one of two groups based on the location of the tibial tunnel (anterior vs. posterior) during the surgical procedure. The study population will consist of patients 16-50 years of age, with ACL rupture, who are seeking surgical reconstruction. Patients with active infection, previous ACL surgery, multiple ligament knee injury, previous joint modifying surgery in target knee within 12 months of planned procedure, flexion contracture, valgus alignment, pathologic ligament instability, knee osteoarthritis, inflammatory joint disease, metabolic bone disease (marked bone loss or moderate to severe osteoporosis), comorbidities such as type 1 diabetes, connective tissue disorder, or morbid obesity (BMI ≥35) will be excluded.

Subjects will return for follow-up visits at 6, 12, and 24 months post-surgery. If a subject is unable to come to UVA for a follow up visit, a home visit can be arranged with a member of the study team. Note that all data cannot be collected through a home visit, but instead only the subjective outcomes and some aspects of the knee exam can be collected. Follow up will be completed at 24 months for all enrolled subjects. Additionally, subjects with a prior ACL reconstruction who meet all study criteria, may enter the study at any post-operative time point (retrospective aspect of the study).

The primary objective of this study is to collect data on subjective and objective measures of knee related function in subjects with an anterior vs. posterior placed tibial tunnel through 24 months postoperative follow-up.

The primary analysis will compare groups at 24-months post-op with regard to:

- 1. Clinically significant difference of at least 8 points on IKDC score
- 2. Clinically significant difference of at least 2.4 mm knee joint laxity (KT-1000)

Background

1. Provide the scientific background, rationale and relevance of this project.

Although extensive research has been carried out on ACL Femoral Tunnel placement, very little attention has been given to the tibial tunnel. Staubli et al. suggest that the tibial tunnel be placed in the center of the ACL footprint, which they described as being approximately 43% of the way (anterior to posterior) across the proximal tibia at its widest extent. However, others have suggested that a more anterior placement may yield improved biomechanical and clinical results. The center of the ACL footprint and the posterior aspect of the anterior horn of the lateral meniscus does not yield tibial tunnel placement a consistent percentage of the way across the tibial plateau⁴, therefore, guidelines should be based on intraoperative fluoroscopic measurements. However, the question remaining is what percentage of the A-P distance across the tibia is the ideal location for the tibial tunnel in ACL reconstruction. This study will help answer that question.

Page 4 of 41

Hypothesis to be Tested

Objective:

Compare anterior versus posterior tibial tunnel placement for ACL reconstruction in a prospective randomized clinical trial.

Hypotheses:

A more anterior placed tibial tunnel will yield improved outcomes with regard to:

- 1. Improved knee-specific self-reported function (IKDC)
- 2. Decreased knee joint laxity (KT-1000)

Study Design: Biomedical

- 1. Will controls be used? No
- 2. What is the study design?

Single-blind, randomized controlled clinical trial

3. Does the study involve a placebo? No

Human Participants

Ages: 16-50

Sex: Male and Female

Race: All

Subjects- see below

INSTRUCTIONS: For question 1-4 below insert an exact #. Ranges or OPEN is not allowed. This # should be the maximum # you expect to need to enroll (i.e. sign consent) If you are only collecting specimens the number of participants should equate to the # of specimens you need. If you are collecting only data from a chart review the number should designate the number of subjects whose medical records you plan to review. Age/ Sex/Race criteria should designate the demographics of participants from whom you will obtain the specimen/data.

- **1.** Provide target # of subjects (at all sites) needed to complete protocol.75(prospective aspect) 45 for retrospectice (UVA only)
- 2. Describe expected rate of screen failure/ dropouts/withdrawals from all sites.

We expect up to a 20% rate of attrition due to loss of follow up.

- 3. How many subjects will be enrolled at all sites? 90- prospective, 45-retrospective (UVA only)
- **4.** How many subjects will sign a consent form under this UVa protocol? Between Jordan-Young Institute and UVA up to 90 subjects will sign consent for the prospective portion of the study—N=55 at UVA. 45

Page 5 of 41

subjects will sign a consent form for the retrospective portion of the study at UVA only. Total of 100 subjects will sign a consent form under this UVA protocol.

5. Provide an estimated time line for the study.

Enrolled subjects will be followed for 2 years post-surgery, or up until 2 years post-operatively for those who enter the study after surgery. We expect 50% enrollment to be achieved within one year, and 100% in two years. We would anticipate completion of follow up to occur in four years.

Inclusion/Exclusion Criteria

INSTRUCTIONS:

The inclusion and exclusion criteria should be written in bullet format.

If this is a collection of only retrospective* specimens or data, the inclusion criteria must include a start and stop date for when specimens/ data will be collected.

The stop date must be prior to the version date of this protocol.

*Retrospective: all specimens are in a lab at the time this protocol is approved by the IRB. All data exists in medical records or records from previous studies at the time this protocol is approved by the IRB.

1. List the criteria for inclusion

- Age at time of randomization or initial surgery: 16 50 years (skeletally mature)
- Primary, uncomplicated ACL reconstruction
- Autograft (STG or BPTB)

2. List the criteria for exclusion

- Multiple ligament knee injury (full thickness)
- Revision ACL reconstruction
- ACL reconstruction with allograft
- Meniscectomy > 75%
- Treatable articular cartilage lesions (debridement acceptable)
- Diagnosis of tibiofemoral or patellofemoral osteoarthritis (Kellgren Lawrence grade > II)
- Valgus knee alignment (weight bearing line outside of joint center)
- Prior ligament reconstruction of cartilage repair surgery in either ankle, knee, or hip
- Prior arthroscopic debridement surgery in either ankle, knee, or hip within 12 months
- Clinical evidence of hip disease
- Patellofemoral joint instability
- Significant patellar or tibiofemoral mal-alignment
- BMI > 35
- Type 1 Diabetes Mellitus
- Known connective tissue disorder (e.g. Ehlers-Danlos)
- Peripheral neuropathy
- Neurovascular/ circulatory disorder
- Any form of inflammatory arthritis (e.g. RA, gout, pseudogout, lupus, etc.)

Page 6 of 41

- Significant co-morbid conditions as determined by the investigator (e.g. malignancy, renal, hepatic disease, etc.)
- Known or suspected psychological disorder
- 3. List any restrictions on use of other drugs or treatments. N/A

Statistical Considerations

1. **Is stratification/randomization involved?** Yes.

► IF YES, describe the stratification/ randomization scheme.

Block randomization will be completed *a priori* via a random number generator. 20 subjects will be allocated to group within each block (10 per group). Group assignments will be sealed in an opaque envelope each containing a number from 001-090. Each subject will be randomly assigned in a 1:1 ratio to receive one of the treatments (group) described below. Randomization envelope #001 will be used for the first subject, #002 for the second and so on. Group assignment for enrolled subjects will be determined intra-operatively. Prior to the determination of group assignment, the treating surgeon will drill two tibial tunnel guide pins, assessing pin placement via fluoroscopy, to ensure that one tunnel is anterior and the other is posterior to the 35% line. The sealed envelope will then be opened following confirmation of guide pin placement, and the procedure will be performed in accordance with the randomized group assignment.

Patients with a prior history of ACL reconstruction who enter the study post-operatively will be assigned to the appropriate group based on graft placement (anterior or posterior) that was performed for clinical care.

► IF YES, who will generate the randomization scheme?

X Other: Study coordinator

2. What are the statistical considerations for the protocol?

We have designed the study in a way that will make it easy to match an appropriate statistical procedure to test our primary hypotheses. Subjective and objective measures of knee function will be evaluated at 6, 12 and 24 months post-surgery.

3. Provide a justification for the sample size used in this protocol.

Sample size for IKDC and KT-1000 side-side differences are calculated based on the expected between-group differences observed at the final time point of this study – 24 months post reconstruction. In order to observe a 2.4 mm between group differences in joint laxity symmetry, we need 40 patients per group. This estimate accounts for up to 3.5 mm in variability in KT-1000 side-side measurement change from pre-post-surgery. Further, we need 55 patients per group to detect a 8-point difference in IKDC score between groups assuming variability of 12 points in IKDC score. These estimates account for 20% attrition. Estimates are calculated to find statistically significant differences allowing for 5% type I error rate and power exceeding 80%.

4. What is your plan for primary variable analysis?

We will use independent t tests to determine group differences at each time point.

Page 7 of 41

5. What is your plan for secondary variable analysis?

We do not plan to use a secondary variable analysis.

6. Have you been working with a statistician in designing this protocol? Yes **IF YES, what is their name?** [name]

Page 8 of 41

- 7. Will data from multiple sites be combined during analysis? Yes
 - 7(a). Does the study involve randomization? Yes

IF YES, will randomization be done at each site or among sites? Randomization will be done at each site.

- 7(b). Has the sample size calculation considered the variation among sites? Yes
- 7(c). When combining the data from multiple sites to assess the study results, is the effect of the treatment to be tested (or the association to be tested) assumed to be the same across sites or vary among sites? What is the modelling strategy?

Yes. The effect of the treatment (placement of tibial tunnel) will be assessed using standard measures of joint laxity and patient-reported function. We have no evidence to believe that these outcomes differ between sites under standard protocols.

7(d). Is there a common protocol used in all sites? NO

IF NO, how will differences among sites, such as those related to the implementation, inclusion criteria, patient characteristics, or other sites characteristics, be considered to assess the study results?

Potential subjects will be identified, screened, and eligibility criteria reviewed in a similar manner at each institution. Each practice will follow the same criteria for enrollment. Statistical considerations will be employed following the completion of data collection to account for differences in patient characteristics/ demographics.

Biomedical Research

1. What will be done in this protocol?

Study Procedures:

All procedures apply to subjects who enter the study prior to surgery.

Screening visit (Visit 1)

After written informed consent is obtained, initial screening will consist of a thorough medical history and physical examination. Special attention will be given to inclusion and exclusion criteria as listed above. Only patients who meet all inclusion and exclusion criteria will be allowed to continue to baseline outcomes data collection. The following subjective outcomes and clinical examination data will be collected at each session.

Subjective Outcomes (10 minutes)

- International Knee Documentation Committee (IKDC) Subjective Knee Evaluation
- Marx Activity Rating Scale

Page 9 of 41

X-ray (15 minutes)

Standing 2-view (posterior-anterior, lateral)

Clinical Evaluation (10 minutes)

- Knee joint laxity with KT-1000
- Knee joint range of motion
- Thigh circumference (15 cm above knee cap)

Surgery (Visit 2)

• Record surgical details: procedure(s) performed, time of procedure, tunnel diameter, tunnel placement details, other arthroscopic findings pertinent to case

Follow Up Visits (Visits 3-5)

Subjects who enter the study after surgery will complete the visits below based upon when they enter the study from their surgery date. If subjects are unable to come to UVA for the follow up visits, it is possible to arrange a home visit with a member of the study team to collect outcomes. Please note that we can only collect questionnaires and the KT-1000 ligament laxity measurement of the knee exam through a home visit.

- 6 months (approximately 182 ± 14 days following surgery)
 - Review of criteria for enrollment
 - Record adverse events
 - Clinical evaluation
 - KT-1000 Ligament Laxity Assessment Questionnaires
 - Marx Activity Scale
 - IKDC Subjective Questionnaire
- 12 months (approximately 364 ± 21 days following surgery)
 - Record adverse events
 - Standing 2-view (posterior-anterior, lateral) x-ray
 - Clinical evaluation
 - o KT-1000 Ligament Laxity Assessment
 - Questionnaires
 - Marx Activity Scale
 - IKDC Subjective Questionnaire
- 24 months (approximately 728 ± 28 days following surgery)
 - Record adverse events
 - Standing 2-view (posterior-anterior, lateral) x-ray
 - Clinical evaluation
 - KT-1000 Ligament Laxity Assessment

Page 10 of 41

- Questionnaires
 - Marx Activity Scale
 - IKDC Subjective Questionnaire
- Quadriceps strength testing (15 minutes) (optional)
 - Maximal, normalized isometric knee extension force (Nm/kg)
 - Quadriceps central activation ratio (%)
- o Gait Analysis (60 minutes) (optional)
 - Kinematic and kinetic analysis during walking and jogging
- 2. List the procedures, in bullet form, that will be done for research as stipulated in this protocol.
 - Screening
 - Subjective Outcomes
 - Marx Activity Scale
 - IKDC Subjective Questionnaire
 - Clinical Examination
 - KT-1000 Ligament Laxity Measurement
 - Quadriceps Strength Assessment
 - Gait Analysis
 - Surgical procedure (surgery is clinical care placement of tibial tunnel is study related)
 - Standing 2-view (posterior-anterior, lateral) x-ray s-3 total

Patients who enter the study post-operatively will be screened in the same manner as those who enter pre-operatively, and all study procedures will be completed accordingly.

- 3. Will you be using data/specimens in this study that were collected previously, with the use of a research consent form, from another research study? No
- 4. Will any of the procedures listed in item # 2 have the potential to identify an incidental finding? Yes, x-ray
 - X The examination(s) utilize(s) the same techniques, equipment, etc., that would be used if the subject were to have the examination(s) performed for clinical care. There exists the potential for the discovery of clinically significant incidental findings.
 - The PI takes full responsibility for the identification of incidental findings:
 - The PI will inform the subjects verbally of all incidental findings that are of clinical significance or are of questionable significance.
 - A follow-up letter describing the finding should be provided to the subject with instructions to either show the letter to their PC or if the subject has no PCP, the subject should be instructed to make an appointment at UVa or at the Free Clinic.

- 5. Do any of the procedures listed above, under question # 2, utilize any imaging procedures? Yes IF YES, list procedures: X-ray
 - ► IF YES, check one of the following two options:
 - **X**_This imaging research examination utilizes the same imaging techniques, equipment, scanning sequences that would be used if the subject were to have the imaging performed for clinical care. There exists the potential for the discovery of clinically significant incidental findings.
 - ► If checked, answer the following:

Will the images be read by a licensed radiologist and the reading placed in the subject's medical record? Yes

- 6. Will you be using viable embryos? No
- 7. Will you be using embryonic stem cells? No
- 8. Are any aspects of the study kept secret from the participants? Yes
 - ► IF YES, describe:

Group assignment will remain confidential until the end of the study

- 9. Is any deception used in the study? No
- 10. If this protocol involves study treatment, explain how a subject will be transitioned from study treatment when they have completed their participation in the study.

All subjects will be prescribed the same rehabilitation program and guidelines in accordance with the standard of care post ACL reconstruction procedure. Participating in this study will not affect the care given or prescribed in any way.

Data and Safety Monitoring Plan

INSTRUCTIONS:

If you have any questions completing this section call [name] for assistance.

A Sponsor is defined as entity that will receive data prior to publication.

- 1. Definition:
 - 1.1 How will you define adverse events (AE)) for this study?
 - __X__An adverse event will be considered any undesirable sign, symptom or medical or psychological condition **even if the event is not considered to be related** to the investigational drug/device/intervention. Medical condition/diseases present before starting the investigational drug/intervention will be considered adverse events only if they worsen after starting study treatment/intervention. An adverse event is also any undesirable and unintended effect of

Page 12 of 41

research occurring in human subjects as a result of the collection of identifiable private information under the research. Adverse events also include any problems associated with the use of an investigational device that adversely affects the rights, safety or welfare of subject s.

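### At the stated maximum of 20% attrition, 90 prospective consents give at most 72 completers rather than 75, and the plan makes no allowance for loss between consent and randomisation

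*Combined protocol and SAP*

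**What the plan says.** All references are to the combined protocol and SAP.

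- **Human Participants, form instruction for items 1-4.** The counts are maxima, and enrolment means consent: "This # should be the maximum # you expect to need to enroll (i.e. sign consent".
- **Item 1.** The prospective number needed to complete is 75: "Provide target # of subjects (at all sites) needed to complete protocol.75(prospective aspect".
- **Item 2.** The form asks the team to "Describe expected rate of screen failure/ dropouts/withdrawals from all sites". The answer is "We expect up to a 20% rate of attrition due to loss of follow up". It gives no screen-failure rate.
- **Items 3 and 4.** Prospective enrolment is 90 across both sites, and "up to 90 subjects will sign consent for the prospective portion of the study".
- **Biomedical Research, item 1, Screening visit.** "After written informed consent is obtained, initial screening will consist of a thorough medical history and physical examination". Patients who do not meet all criteria do not go on to baseline data collection.
- **Statistical Considerations, item 1.** Envelopes are numbered 001-090. Two guide pins are placed in surgery, and "The sealed envelope will then be opened following confirmation of guide pin placement".
- **Statistical Considerations, item 3.** The plan requires 40 per group for KT-1000 (2.4 mm, variability 3.5 mm) and 55 per group for IKDC (8 points, variability 12). Both are said to include 20% attrition, with a 5% type I error rate and power above 80%.

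**The concern.** There are two gaps in the chain from consent to completion.

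The first is arithmetic. The 75, the 20% and the 90 do not fit together, because 20% loss from 90 does not leave 75.

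The second is an omission. The 90 counts signatures, and a signature comes before the study's own screening examination and before the envelope is opened. Two exclusion criteria (meniscectomy above 75%, and treatable cartilage lesions) may be settled only at operation. The Recruitment appendix, item 4, allows nothing beyond answering questions before consent. Some loss between consent and assignment is therefore to be expected. Ninety envelopes for at most 90 consents leaves no room for it.

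At stake is whether the stated completers and power describe the trial that 90 consents would produce.

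**Working it through.** **Inputs from the protocol.** Consent ceiling 90; target completers 75; attrition up to 20%; 1:1 allocation; IKDC difference 8 with SD 12; KT-1000 difference 2.4 mm with SD 3.5 mm; type I error 5%.

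**Assumptions.** The test is two-sided (sidedness is not stated). Patients split equally between groups. Only randomised patients are counted. The fraction lost between consent and randomisation, s, is not given in the documents, so a range is shown.

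**1. Reproducing the plan's 90.** 75 x 1.20 = 90, which matches exactly. The protocol does not show its derivation, so this source is an inference. To retain 75 after a 20% loss, the calculation is 75/(1 - 0.20) = 93.75, so 94.

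**2. Forward check.** 90 x (1 - 0.20) = 72, which is 3 short of 75.

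**3. Power at 72 completers, 36 per group.** The standardised differences are 8/12 = 0.667 and 2.4/3.5 = 0.686. Noncentral t power is 79.7% for IKDC and 81.8% for KT-1000. The normal approximation gives 80.7% and 82.9%. With 75 completers (37.5 per group), the t-test values would be 81.3% and 83.4%.

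**4. Adding loss before randomisation.** Randomised = 90(1 - s). Completers = 90(1 - s) x 0.80. Consents needed for 75 completers = 75/[0.80(1 - s)], rounded up. Power uses the unrounded expected number per group.

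| s (assumed) | Randomised | Completers | Power IKDC | Power KT-1000 | Consents needed for 75 |
|---|---|---|---|---|---|
| 0% | 90 | 72 | 79.7% | 81.8% | 94 |
| 5% | 85.5 | 68.4 | 77.5% | 79.8% | 99 |
| 10% | 81 | 64.8 | 75.2% | 77.6% | 105 |
| 15% | 76.5 | 61.2 | 72.7% | 75.1% | 111 |
| 20% | 72 | 57.6 | 70.1% | 72.5% | 118 |

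**5. When 75 is still reached.** All losses together must be at most 90 - 75 = 15, and 15/90 = 16.7%. The largest follow-up attrition that still leaves 75 is 1 - 75/[90(1 - s)]: 16.7% at s = 0, 12.3% at 5%, 7.4% at 10% and 2.0% at 15%.

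**6. Against the sample-size paragraph.** 2 x 55 = 110 patients are required for IKDC with attrition already included. That exceeds 90 whatever s is.

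**The case against.** The strongest reply is that the demonstrable shortfall is three patients and costs little power. That is right: at s = 0 the IKDC figure misses 80% only on the exact t calculation, and KT-1000 stays above it. Every larger loss in the table comes from an assumed rate.

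Several stronger readings are tempting, and the documents do not support them.

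- **That 75 completers cannot be reached.** The 20% is stated as a maximum. 75 is reached if losses of all kinds total 15 or fewer.
- **That the shortfall arises because consent comes first.** It is already there with no screen failures. The order of events can only enlarge it.
- **That no eligibility check precedes consent.** The Recruitment appendix includes review of records to determine eligibility, and the protocol's opening summary limits prospective candidates to patients already scheduled for reconstruction. This should lower screen failure after consent, but it does not replace the screening visit.
- **That a failed pin check removes patients.** The protocol says the surgeon places the pins so that one lies on each side of the 35% line. It describes no failure and no exclusion.
- **That recruitment must stop with envelopes unused.** The consent count can be amended.
- **That the post-operative part has the same fault.** Its 45 to enrol and 45 to complete also leave nothing for loss, but it has no envelope or pin check, so that is a separate matter.

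Two further cautions stand. The form instruction says items 1-4 count consents, while item 1 asks for the number needed to complete, so the meaning of 75 should be confirmed. The post-operative entrants are assigned to the same two groups, and the protocol does not say that they are analysed separately. The power figures here concern the randomised patients alone.

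**Conclusion.** The stated figures are inconsistent as written. Under the protocol's own maximum attrition, 90 consents deliver at most 72 completers, 3 fewer than stated. IKDC power is then 79.7% and KT-1000 power 81.8%, against an aim of more than 80%. This part rests only on the protocol's figures, a two-sided t test and equal groups.

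The missing allowance between consent and randomisation is also established: item 2 asks for screen failures and answers only with follow-up loss, and the envelopes equal the consent ceiling. Its size is not established. At an assumed 5-10% loss, completers would be about 68-65 and power about 78-75% for IKDC and 80-78% for KT-1000. The conclusion is that completers and power are overstated at 20% attrition and have no margin. It is not that the target is out of reach.

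**What to change.** Keep Human Participants items 3 and 4 as counts of consents, since item 4 asks for exactly that. In items 1 and 2 and in the sample-size paragraph, state:

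- an assumed rate of loss between consent and randomisation, beside the 20% follow-up loss;
- the expected number randomised from 90 consents;
- the expected completers (72 or fewer at 20% attrition) in place of 75;
- the resulting power for each endpoint, for example 81 randomised, about 65 completers and about 75% / 78% at an assumed 10% loss.

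Reconcile these with the 55-per-group requirement in Statistical Considerations, item 3, because settling that conflict may change the 90, the 75 and the envelope list together.

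Counting the 90 at envelope opening would not be enough, because 90 randomised still gives 72 at 20% attrition. Keeping 75 would need 94 randomised and a higher consent ceiling.

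The cost is a revision of wording and a slightly less favourable stated figure for completers and power. Treatment, visits and the consent ceiling need not change for the restatement itself.

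### Graft type (STG or BPTB) need not be recorded before the envelope is opened and is left out of the primary t test: a modest loss of precision, and a bias only if graft choice could follow assignment

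*Combined protocol and SAP*

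**What the plan says.** The document is the combined protocol and SAP.

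- **Eligibility** (Inclusion/Exclusion Criteria, items 1 and 2). Inclusion lists "Autograft (STG or BPTB". Exclusion lists "ACL reconstruction with allograft". Either autograft may therefore be used in either arm.
- **Randomisation** (Statistical Considerations, item 1). "20 subjects will be allocated to group within each block (10 per group"; "Each subject will be randomly assigned in a 1:1 ratio". The group is revealed during surgery: the surgeon drills two guide pins and checks them by fluoroscopy, and "The sealed envelope will then be opened following confirmation of guide pin placement". Pin confirmation is the only step required first. Item 7(a) adds "Randomization will be done at each site". Graft appears nowhere in the scheme.
- **Analysis** (Statistical Considerations, items 4 and 5). "We will use independent t tests to determine group differences at each time point". No secondary analysis is planned.
- **Later adjustment** (answer to item 7(d)). Differences between patients are to be allowed for in some way after data collection. No method and no variable is named; graft is not mentioned.
- **Data collected at surgery** (Biomedical Research, item 1, Visit 2). "Record surgical details: procedure(s) performed, time of procedure, tunnel diameter, tunnel placement details", plus other pertinent arthroscopic findings. Graft type is not a named item.
- **Retrospective patients** (Statistical Considerations, item 1). The 45 patients who enter after surgery are grouped by the placement they received, not by randomisation.

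**The concern.** Graft is a surgical choice made close to the moment of allocation, and the surgeon who completes the operation has just seen the assignment. There are two cases.

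- **Graft settled before the envelope.** It is then a baseline variable. Randomisation balances it on average, and any chance imbalance is covered by the 5% error rate. What is lost is precision: if the two grafts differ in outcome, that variation stays in the error term.
- **Graft chosen or changed after the envelope.** It is then a post-randomisation variable. A difference in graft mix between arms could follow from the assignment, and an unadjusted comparison would attribute its effect to tunnel position.

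The plan does not say which case applies. The planned record may show which graft was used, but not whether it was chosen before the assignment was known.

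**Working it through.** **Inputs from the protocol.** 90 prospective patients at 1:1 gives 45 per arm; 20% attrition leaves 45 × 0.8 = 36. Targets are 8 points (IKDC) and 2.4 mm (KT-1000). The stated variability of 12 points and 3.5 mm is taken as the SD. Type I error is 5%.

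**Assumptions.** A two-sided test (sidedness is not stated), a 50/50 graft share, and a graft effect g of 3 or 5 points on IKDC and 1 or 2 mm on KT-1000. The documents give neither a graft share nor a graft effect.

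**The plan's own figures.** The plan gives no figure on graft. Its sample sizes, including attrition, are 40 per group (KT-1000) and 55 (IKDC). The usual formula at 80% power gives 34 and 36 completers, or 34/0.8 ≈ 43 and 36/0.8 = 45 enrolled. The 40 is close if attrition is applied as n × 1.2 (41). The 55 is not reproduced at exactly 80%, but 55 × 0.8 = 44 completers give about 87% power, which fits a claim of power above 80%. Nothing below depends on this.

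**Step 1: power of the planned t test.** Noncentrality λ = Δ / (σ√(2/n)), with √(2/36) = 0.2357 and 70 degrees of freedom.

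- IKDC: 8 / (12 × 0.2357) = 2.828, power 79.7%
- KT-1000: 2.4 / (3.5 × 0.2357) = 2.909, power 81.8%

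**Step 2: power with graft as a factor.** Residual variance = σ² − 0.25g², with 69 degrees of freedom and equal graft mix in the two arms.

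| Outcome | g | Residual SD | λ | Power |
|---|---|---|---|---|
| IKDC | 3 points | √(144 − 2.25) = 11.906 | 2.851 | 80.3% |
| IKDC | 5 points | √(144 − 6.25) = 11.737 | 2.892 | 81.4% |
| KT-1000 | 1 mm | √(12.25 − 0.25) = 3.464 | 2.939 | 82.6% |
| KT-1000 | 2 mm | √(12.25 − 1) = 3.354 | 3.036 | 84.9% |

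If graft has no effect, the lost degree of freedom costs under 0.1 point of power.

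**Step 3: allowance for chance imbalance.** In an adjusted model, imbalance in graft multiplies λ by √(1 − r²), where r is the correlation of graft with arm. Under randomisation r² averages 1/(72 − 1) = 1.4%, a factor of 0.993. Average power is then 79.7% and 80.8% for IKDC (g = 3, 5) and 82.1% and 84.4% for KT-1000 (g = 1, 2). With no graft effect it is 79.1% and 81.3%. At the low end of the assumed effects the net gain is close to nil.

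**Step 4: size of a chance gap in graft share.** SD = √(2 × 0.25/36) = 11.8 percentage points. From two independent binomials (36, 0.5), a gap of 10 points or more occurs in 41% of trials, 15 or more in 19.5%, and 20 or more in 7.6%. This does not invalidate the test. In 6,000 simulated trials per setting with graft fixed before allocation and no tunnel effect, the unadjusted and adjusted tests rejected 4.6-5.1% of the time.

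**Step 5: the conditional case.** If graft share differed systematically between arms because choice followed assignment, shift = gap × g. Gaps of 20 and 30 points are illustrations; nothing in the documents suggests either. The last column is the rejection rate of the planned t test with no tunnel effect.

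| Gap | Outcome | g | Shift | Rejection rate |
|---|---|---|---|---|
| 20 points | KT-1000 | 1 / 2 mm | 0.2 / 0.4 mm | 5.7% / 7.7% |
| 20 points | IKDC | 3 / 5 points | 0.6 / 1.0 points | 5.5% / 6.4% |
| 30 points | KT-1000 | 1 / 2 mm | 0.3 / 0.6 mm | 6.5% / 11.1% |
| 30 points | IKDC | 3 / 5 points | 0.9 / 1.5 points | 6.1% / 8.2% |

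**The case against.** A reader might infer that graft mix will differ between arms and be reported as a tunnel effect. The documents do not support that. No section says that the graft is chosen or changed after the envelope. An autograft plan is part of eligibility, which is reviewed at Visit 1, although either graft meets the criterion. The list of research procedures treats the surgery as clinical care and only the tunnel placement as study related. The envelope is opened mid-operation, which leaves a narrow window, and no reason is given why tunnel position should change the graft. What stands is that the bias is possible but not shown.

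A reader might also take the exclusion of allograft as evidence that the two autografts are known to differ in outcome. It is not. The graft effects used here are assumptions, and larger ones would have to match or exceed the trial's own target differences.

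Nor may one infer that graft would go uncaptured. The Visit 2 entry for procedures performed may hold it, and for UVA patients the Clinical Data Repository appendix also selects procedures and narrative reports, a category that includes operative notes. What these sources are not set up to show is whether the choice came before the envelope.

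Finally, other baseline factors could be adjusted for too, and item 7(d) promises some later adjustment. Graft differs in that it is a surgical choice made close to allocation. An adjustment decided after data collection, with no named variable or method, does not replace a pre-specified one.

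**Conclusion.** The point holds as a cheap improvement, not as a demonstrated flaw. If the graft is in practice settled before the envelope, the planned t test is unbiased and keeps its 5% error rate. The loss is then at most 0.6-1.7 points of power for IKDC (graft gap 3-5 points) and 0.8-3.1 points for KT-1000 (gap 1-2 mm). After allowance for chance imbalance it is about 0-1.1 and 0.3-2.6 points. These figures rest on 36 completers per arm, the plan's SDs, a two-sided 5% test and an assumed equal graft split.

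Bias arises only if the graft can depend on the revealed assignment. The plan neither describes nor excludes this, and as written it would leave no record by which to check.

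**What to change.** 1. **Statistical Considerations, item 1.** Require the intended graft type (STG or BPTB, as chosen for clinical care) to be recorded on the case report form before the envelope is opened. In the Visit 2 surgical details, name graft type as an item, so that intended and used graft can be compared. The early record does not prevent a later change, but it makes one visible.
2. **Statistical Considerations, item 4.** Pre-specify the pre-envelope graft type as a fixed factor in the 24-month IKDC and KT-1000 comparisons, and report graft mix by arm.
3. **Population.** Limit this adjusted comparison to the randomised patients. The 45 retrospective patients cannot have a pre-envelope record and were not randomised.

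**Cost.** One form field, one sentence in the randomisation procedure and one model term. If graft has no effect, the degree of freedom costs under 0.1 point of power, or about 0.6 point in all once chance imbalance is averaged in. No extra patients, visits or procedures are needed, and the choice of graft is left as it is.
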